9.10. Pharmacokinetic Analysis

9.10.1. Sample Collections for Pharmacokinetic Analysis

Blood samples for the PK analysis will be obtained at baseline (prior to study drug administration); at 5, 15, and 30 minutes; and at 1, 2, 4, 6, 8, 12, 16, and 24 hours after study drug administration for all treatment groups. Additional blood samples will be collected at 36, 48, 60, 72, and 96 hours after study drug administration for DepoTXA-treated subjects.

9.10.2. Pharmacokinetic Parameter Calculation Methods

Pharmacokinetic parameters will be calculated by a noncompartmental analysis method from concentration-time data using WinNonlin Professional (Version 5.2 or later) or SAS following these guidelines:

- Actual sampling times relative to study drug administration will be used for all calculations of the PK parameters. If there is any doubt as to the actual time a sample was taken, then the scheduled time will be used. Descriptive statistics will be used to summarize the PK parameters.
- Concentrations from unscheduled PK blood samples will be used in the analysis of the parameters.
- There will be no imputation of missing data.

For the calculation of AUC from PK concentrations, concentration below the limit of quantification (BLOQ) will be handled as follows:

- Pre-dose values will be set to zero.
- All remaining BLOQ values will be set to missing.

Pharmacokinetic parameters will be estimated according to the following guidelines:

- The maximum observed plasma concentration (C_{max}) will be obtained directly from the concentration-time data.
- Time to maximum concentration (T_{max}) is the time at which C_{max} is observed.
- The apparent terminal elimination rate constant (λ_z) will be estimated at terminal phase by linear regression after log-transformation of the concentrations:
 - Only those data points that are judged to describe the terminal log-linear decline will be used in the regression.
 - A minimum number of three data points in the terminal phase will be used in calculating λ_z with the line of regression starting at post- C_{max} data point (C_{max} should not be part of the regression slope) and including C_{last} and t_{last} .
 - The adjusted correlation coefficient (R^2 adjusted) in general should be greater than 0.90. Any value less than 0.90 may be used according to the pharmacokineticist's best knowledge and judgment.
 - An appropriate number of decimal places should be used for λ_z for an precise calculation of the of half-life ($t_{1/2}$).
- Half-life ($t_{1/2}$) will be calculated as $\ln(2)/\lambda_z$.
- AUC will be calculated as follows:
 - The linear trapezoidal method will be employed for all incremental trapezoids arising from increasing concentrations and the logarithmic trapezoidal method will be used for those arising from decreasing concentrations.
 - $AUC_{(0-t)} = \int_0^t C(t)dt$
 - $AUC_{(0-\infty)} = \int_0^t C(t)dt + \int_t^\infty C(t)dt = AUC_{(0-t)} + C_t / \lambda_z$
- C_t is last observed quantifiable concentration.

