9.10.3. Pharmacokinetic Concentrations and Variables

The analysis of the PK data will be based on the PK analysis set.

TXA plasma concentrations will be listed by treatment group, subject, nominal time, and actual time. Concentrations that are BLOQ will be indicated by BLOQ in this listing.

Plasma concentrations will be summarized by treatment at each time point. The following descriptive statistics will be presented for plasma concentrations obtained at each nominal time point: n, arithmetic mean, SD, coefficient of variation (%CV), geometric mean, median, minimum and maximum.

Pharmacokinetic parameters will be summarized for each treatment group. Descriptive statistics for calculated PK parameters will include: n, arithmetic mean, SD, %CV, geometric mean,

median, minimum and maximum values. Geometric mean will not be presented for T_{max} . Values of %AUC extrapolated > 20% will be flagged in the listings.

Individual plasma concentration versus actual times will be plotted by treatment in linear and semi-logarithmic scale.

The geometric mean ratios (GMRs) for DepoTXA 400 mg, DepoTXA 800 mg, and DepoTXA 1200 mg to IV TXA will be presented separately along with their corresponding 95% confidence intervals for AUC_{0-t} and C_{max} .

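### For AUC, BLOQ samples before the first quantifiable concentration are dropped, not set to zero, so an absorption lag is credited with exposure; the concentration summaries have no BLOQ rule at all

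*SAP*

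**What the plan says.** The BLOQ rule in SAP section 9.10.2 opens with its scope: "For the calculation of AUC from PK concentrations, concentration below the limit of quantification (BLOQ) will be handled as follows". Two instructions follow: "Pre-dose values will be set to zero" and "All remaining BLOQ values will be set to missing". The second covers every post-dose BLOQ sample, whether it comes before the first quantifiable value, between two quantifiable values, or after the last one.

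The same section adds "There will be no imputation of missing data" and, for the area itself, "The linear trapezoidal method will be employed for all incremental trapezoids arising from increasing concentrations". Falling segments use the logarithmic trapezoid. The area ends at the last measurable sample: "C_t is last observed quantifiable concentration".

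Section 9.10.3 then says "Plasma concentrations will be summarized by treatment at each time point", and lists n, arithmetic mean, SD, %CV, geometric mean, median, minimum and maximum. Its only BLOQ instruction concerns display: "Concentrations that are BLOQ will be indicated by BLOQ in this listing". The shell for Table 14.4-2 and the entries for the mean concentration figures add no rule. Section 9.10.3 also calls for the geometric mean ratio of each DepoTXA dose to IV TXA, with a 95% confidence interval, for AUC0-t and Cmax.

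**The concern.** There are two separate issues.

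**AUC.** When a post-dose sample is BLOQ, the plan has a measurement saying that little or no drug was present. Treating it as missing discards that information. The trapezoid then joins zero at dosing to the first quantifiable value and gives area to the interval in between. An absorption lag is plausible for a locally placed depot but not for IV dosing, so the effect is unlikely to cancel between arms. It enters AUC0-t, and through it the DepoTXA/IV ratios that serve the primary objective in section 5.1.

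**Summaries.** Section 9.10.3 orders statistics at each nominal time without saying what a BLOQ sample contributes. Someone must choose, because text cannot be averaged and a geometric mean cannot take zeros. If the AUC rule were carried over, late DepoTXA means would rest only on subjects who are still quantifiable.

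**Working it through.** The SAP states no quantification limit, lag or expected BLOQ rate, so there is no figure of its own to reproduce. The sampling times (section 9.10.1) and the trapezoid rule (section 9.10.2) are the plan's. Everything marked as assumed is not.

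**1. Early area.** Let C1 be the first quantifiable concentration at time t1, and t0 the time of the last leading BLOQ sample.

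- Plan's rule (BLOQ dropped): 0.5 × t1 × C1.
- Leading BLOQ set to zero: 0.5 × (t1 − t0) × C1.
- Excess: 0.5 × t0 × C1.

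| First quantifiable sample | Dropped | Set to zero | Excess | Ratio |
|---|---|---|---|---|
| 15 min | 0.125 C1 h | 0.083 C1 h | 0.042 C1 h | 1.5 |
| 30 min | 0.25 C1 h | 0.125 C1 h | 0.125 C1 h | 2 |
| 1 h | 0.5 C1 h | 0.25 C1 h | 0.25 C1 h | 2 |
| 2 h | 1.0 C1 h | 0.5 C1 h | 0.5 C1 h | 2 |
| 4 h | 2.0 C1 h | 1.0 C1 h | 1.0 C1 h | 2 |
| 6 h | 3.0 C1 h | 1.0 C1 h | 2.0 C1 h | 3 |

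Against the zero rule the excess is always positive. Against the true curve, the line drawn by the plan passes through C1 × t0/t1 at the last BLOQ sample. With t0 = 1 h and t1 = 2 h that is C1/2, which overstates the measured sample whenever C1 is more than twice the limit.

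**2. Share of total AUC.** Take samples BLOQ to 1 h and C1 at 2 h, so the excess is 0.5 C1 h. If AUC is assumed to be 20 C1 h, 0.5/20 = 2.5%. If it is assumed to be 50 C1 h, 0.5/50 = 1%.

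**3. Whole profiles.** These are assumed one-compartment curves with a lag, a limit of 1 on a scale of 100, and the plan's sampling times and trapezoids. The slow profile has absorption and elimination constants of 1 and 0.05 per hour; the fast one has 1.5 and 0.3. The table shows the rise in AUC0-t over the zero rule.

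| Assumed lag | First quantifiable | Slow | Fast |
|---|---|---|---|
| 0.1 h | 15 min | 0.03% | 0.25% |
| 0.3 h | 30 min | 0.12% | 0.97% |
| 0.6 h | 1 h | 0.42% | 3.3% |
| 1.2 h | 2 h | 1.4% | 9.6% |
| 2.5 h | 4 h | 3.8% | 21.3% |

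The 1.2 h row agrees with step 2. In the fast profile the excess is 346.4 − 316.1 = 30.3, so C1 = 30.3/0.5 = 60.6 and AUC is only 316.1/60.6 = 5.2 C1 h, well below the 20 to 50 assumed there.

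**4. Trailing BLOQ.** AUC0-t stops at the last quantifiable value, so samples after it add nothing, whether dropped or not.

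**5. Summaries, only if the AUC rule were carried over.** With k of 15 subjects quantifiable, the quantifiable-only mean is exactly 15/k times the mean with BLOQ counted as zero: 1.25 (k = 12), 1.5 (k = 10), 3 (k = 5). Neither is the true mean. For an assumed lognormal concentration with CV 50% to 100%, in multiples of the limit:

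| Median / limit | True mean | Quantifiable only | BLOQ = 0 |
|---|---|---|---|
| 1 | 1.12 to 1.42 | 1.53 to 2.26 | 0.76 to 1.13 |
| 0.5 | 0.56 to 0.71 | 1.26 to 1.74 | 0.09 to 0.35 |

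A quantifiable-only mean cannot fall below the limit, however low the true concentrations are.

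**The case against.** Four points can fairly be made in the plan's defence.

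- **The AUC effect may be trivial.** The 2 h example needs every sample at 5, 15 and 30 minutes and 1 h to be BLOQ. The programmer note to Table 14.4-1 asks for an early Cmax and Tmax, so an early peak is anticipated, although its timing is not given. This stands as a limit on size. It does not make the rule right.
- **The SAP does not say that late means are taken over quantifiable subjects only.** A reader might infer this from the missing-value rule and from BLOQ appearing as text in the listing. The documents do not support it: the rule is expressly confined to AUC, and the listing instruction is a display convention. The summary rule is undefined, not fixed at a biased choice. This stands in full.
- **The summaries cannot affect the between-arm estimates.** Handling of trailing BLOQ alters neither AUC0-t nor Cmax, and the SAP nowhere states that the 36 to 96 h samples are there to demonstrate prolonged exposure. This also stands; that part concerns descriptive tables and plots.
- **Dropped values would be partly visible.** n falls, Listing 16.2-18.1 shows BLOQ by subject and time, and individual curves are plotted. This is true, but n alone does not separate BLOQ from samples that were not taken.

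**Conclusion.** The AUC point holds. Section 9.10.2 states a rule that, for leading BLOQ samples, can only raise AUC0-t compared with counting them as zero. A lag is plausible for the depot arms and not for IV, so the DepoTXA/IV ratio can be biased upward. A relative excess shared by all subjects of a DepoTXA arm, with none in the IV arm, passes unchanged into that ratio.

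The size is about 1% to 2.5% if samples are BLOQ to 1 h and AUC is 50 to 20 C1 h. It is below 1% in the assumed profiles when the first quantifiable sample comes by 30 minutes. It becomes larger only with a long lag and a small AUC relative to C1. The lag and the limit are not in the SAP, so the true size is unknown.

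The summary point holds as a gap: section 9.10.3 has no BLOQ rule for the statistics and mean plots. The upward bias of quantifiable-only means is what would follow from carrying the AUC rule over. It is not something the plan prescribes.

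**What to change.** In section 9.10.2:

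- Set post-dose BLOQ values before the first quantifiable concentration to zero for AUC.
- Keep BLOQ values after the last quantifiable concentration as missing; this leaves AUC0-t unchanged.
- State a deliberate rule for embedded BLOQ values. They could fall between the early and late peaks named in the note to Table 14.4-1, where the present rule simply bridges them.

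In section 9.10.3:

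- State one BLOQ rule for the summaries and mean plots. For example, count BLOQ as zero in the arithmetic mean and median, and acknowledge that this is biased low.
- Say how the geometric mean is handled, since it cannot take zeros.
- Print the number BLOQ per arm and timepoint in Table 14.4-2, so that any choice can be judged.

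The cost is a few sentences and one table row, with no new data, provided the rule is settled before concentrations are examined. The downside is that DepoTXA AUC and late mean concentrations may come out slightly lower.

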9.10.3. Pharmacokinetic Concentrations and Variables

The analysis of the PK data will be based on the PK analysis set.

TXA plasma concentrations will be listed by treatment group, subject, nominal time, and actual time. Concentrations that are BLOQ will be indicated by BLOQ in this listing.

Plasma concentrations will be summarized by treatment at each time point. The following descriptive statistics will be presented for plasma concentrations obtained at each nominal time point: n, arithmetic mean, SD, coefficient of variation (%CV), geometric mean, median, minimum and maximum.

Pharmacokinetic parameters will be summarized for each treatment group. Descriptive statistics for calculated PK parameters will include: n, arithmetic mean, SD, %CV, geometric mean,

median, minimum and maximum values. Geometric mean will not be presented for T_{max} . Values of %AUC extrapolated > 20% will be flagged in the listings.

Individual plasma concentration versus actual times will be plotted by treatment in linear and semi-logarithmic scale.

The geometric mean ratios (GMRs) for DepoTXA 400 mg, DepoTXA 800 mg, and DepoTXA 1200 mg to IV TXA will be presented separately along with their corresponding 95% confidence intervals for AUC_{0-t} and C_{max} .

9.11. Interim Analysis

No Interim analyses are planned.

10. SAMPLE SIZE CALCULATION

The sample size was not based on statistical considerations.

12. TIME AND EVENTS SCHEDULE OF STUDY PROCEDURES

	Screen Visit ¹	D1 Preop	OR	PACU Arrival	5 min	15 min	30 min	1h	2h	4h	6h	8h	12h	16h	24h	36h	48h	60h	72h	96h	120h	Day 7	D14 Call	D30 Call	D60 Call
	Time Window	Within 30 days			±2 min	±3 min	±5 min	±10 min	±15 min	±15 min	±15 min	±30 min	±30 min	±1h	±1h	±2h	±2h	±2h	±4h	±6h	±6h	±1d	±1d	±3d	±3d
Obtain signed ICF		X																							
Assess/confirm eligibility		X	X																						
Record medical and surgical history		X	X																						
Record demographics and baseline characteristics		X																							
Conduct pregnancy test for WOCBP		X	X																						
Perform physical examination		X																							
Clinical labs (hematology, chemistry) ²		X	X																						X
Coagulation (fibrinogen and fibrin split products)		X	X																						X
Creatinine clearance calculation ²		X																							X
Hemoglobin and hematocrit ²		X	X		X										X	X	X	X	X	X	X	X	X	X	
Perform neurological assessment ³		X	X												X	X	X	X	X	X	X	X	X		
Perform 12-lead ECG recordings ⁴		X						X ⁴							X ⁴										
Measure vital signs ⁵		X	X		X	X	X	X	X	X	X	X	X	X	X	X	X	X	X	X	X	X	X		
Collect NRS-R pain score		X		X					X	X	X	X	X	X	X	X	X	X	X					X	
Collect knee and thigh measurements (both legs)			X																	X ⁶	X ⁶			X ⁶	
Assess surgical wound for SWAS parameters ⁷																				X	X			X	
Collect PK blood sample from all treatment groups; record date and time ⁸			X			X	X	X	X	X	X	X	X	X	X	X	X	X							
Collect additional PK blood samples for DepoTXA treatment groups; record date and time																				X	X	X	X	X	
Randomize patient, prepare study drug			X																						
Administer study drug				X																					
Record start and end time of tourniquet use and max pressure (mm Hg) used					X																				
Record surgery start and stop times						X																			
Perform knee flexion assessment ¹³		X																							
Perform TUG test; record date and time ¹¹		X																							X
Record date and time of discharge																									
Record any blood transfusion data (eg, start and stop times, units)																									
Record any reoperations due to hematoma or wound dehiscence																									
Record prior and concomitant medications ¹²																									
Record whether patient has achieved independent ambulation																									
Record AEs beginning at time ICF is signed ^{2,3,5,8,10}																									

Abbreviations: AE = adverse event; d = day; D = day; ECG = electrocardiogram; h = hours; ICF = informed consent form; max = maximum; min = minutes; OR = operating room; PACU = post-anesthesia care unit; PK = pharmacokinetic; Preop = preoperative; TUG = timed up-and-go; WOCBP = women of childbearing potential.

* Postsurgical assessments will be conducted at the timepoints specified after the beginning of study drug administration.

¹ The screening visit must take place at least 1 day prior to surgery.

² Also conduct clinical laboratory tests if a patient experiences an AE of special interest or a serious AE (SAE), if appropriate; see footnote 10.

³ Also conduct a neurological assessment if a patient experiences an AE of special interest or an SAE, if appropriate; see footnote 10.

⁴ Postsurgical 12-lead ECGs will be performed at 1 hour (± 15 minutes) and 12 (± 2) hours after study drug administration

⁵ Vital signs will be measured after the patient has rested in a supine position for at least 5 minutes. Also measure vital signs if a patient experiences an AE of special interest or an SAE, if appropriate; see footnote 10.

⁶ Collect knee and thigh measurements (both legs) on the morning of postsurgical Day 2.

⁷ The surgical wound will be assessed for the SWAS parameters (wound oozing, erythema, ecchymosis, and blisters) at the time of knee measurements on the morning of postsurgical Day 2 and on Day 7.

⁸ Also collect a PK sample if a patient experiences an AE of special interest or an SAE; see footnote 10.

⁹ Record date and time of all medications starting at least 30 days prior to study drug administration through 120 hours after study drug administration. Record medications administered for treatment of an AE through Day 60 (± 3 days).

¹⁰ Adverse events of special interest include changes in color vision, VTE or PE, and oliguria. If an AE of special interest or serious AE (SAE) occurs during the study, an unscheduled PK blood sample must be collected. In addition, vital signs, the neurological assessment, and clinical laboratory tests should be conducted, as appropriate. If a patient experiences changes in color vision, an ophthalmological consultation must be ordered.

¹¹ Postsurgical “Timed Up-and-Go” will be assessed once on the day of the surgery; at approximately 8:00 am and 8:00 pm (± 2 hours) daily from Day 2 through hospital discharge; and on Day 7.

¹² Each institution may follow its standard protocol for the control of postsurgical pain; however, patient-controlled analgesia is not permitted.

¹³ Each institution may follow its standard protocol for the control of postsurgical pain; however, patient-controlled analgesia is not permitted.

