7. DEFINITIONS

Study Day

Study Day 1 is defined as the day of surgery. Study day is calculated as the date of event minus the date of surgery plus one (1), if the date of event is on or after the date of surgery. Study day is based on the calendar dates, thus days before the date of study drug administration have negative values while those on or after the date of surgery have positive values.

Treatment-emergent Adverse Events

A TEAE will be any adverse event or pre-existing medical condition that worsens in intensity after the start of study drug and within 30 days of the last dose.

Time 0 (zero)

Time 0 is defined as the date and time of the start of study drug administration.

Time Periods

All schedule times have a window associated with them (see Time and Events Schedule in the Protocol for individual timepoint windows). Various time frames that are dependent on these windows are used in the data analyses. Table 1 defines the actual elapsed times with allowance for the windows that can be included in the window.

Table 1: Time Periods

Defined time frame	Acceptable elapsed times
5 min	3-7 min
15 min	12-18 min
30 min	25-35 min
1h	50-70 min
2h	105-135 min
4h	225-255 min
6h	345-375 min
8h	450-510 min
12h	690-750 min
16h	15-17h
24h	23-25h
36h	34-38h
48h	46-50h
60h	57-63h
72h	68-76h
96h	90-102h
120h	114-126h
Study Day 7	Study Day 6-8
Study Day 14	Study Day 13-15
Study Day 30 Call	Study Day 27-33
Study Day 60 Call	Study Day 57-63

If there are two or more data points that fit the time window the data point that occurs the closest, in absolute value, to the scheduled observation will be used.

Baseline

Baseline is defined as the last available measurement or assessment prior to the start of study drug administration.

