9.9. Safety Analyses

The following safety assessments will be summarized:

- 12-lead ECGs at day 1 Preop (D1 Preop), and 1 hour and 12 hours after study drug administration.
- Vital signs (resting heart rate and blood pressure) at Baseline, and 5min, 15min, 30min, 1hr, 2hr, 4hr, 6hr, 8hr, 12hr, 16hr, 24hr, 36hr, 48hr, 60hr, 72hr, and 96hr after study drug administration.
- Neurological assessment at D1 Preop and at 12, 24, 36, 48, 60, 72, and 96 hours after study drug administration.
- Clinical laboratory testing (hematology [including fibrinogen and fibrin split products, lipid profile] and chemistry) at D1 Preop, at 48 hours, and at day 7.
- Creatinine clearance measurement at 48 hours and at day 7.
- Reoperations due to hematoma or wound dehiscence.
- Adverse events through study day 60.

No inferential statistics are planned for any of the safety assessments.

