9.9.1. Electrocardiograms

Investigators will classify ECG tracings as ‘normal’, ‘abnormal not clinically significant’ or ‘abnormal clinically significant’. The investigator classifications will be tabulated by treatment and overall treatments at any time during the study and each assessment timepoint. A shift table comparing the investigator classification of the ECG results at baseline to each scheduled timepoint will also be provided.

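### Table 1 analysis windows at 1 h and 12 h are narrower than the ECG windows in the SAP's own schedule, and no rule says where a compliant ECG outside Table 1 is counted

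*SAP*

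**What the plan says.** Section 7 measures elapsed time from the start of dosing: "Time 0 is defined as the date and time of the start of study drug administration". It then states that "Table 1 defines the actual elapsed times with allowance for the windows that can be included in the window". Table 1 has one row per timepoint, shared by all assessments. The 1 h row is 50-70 min and the 12 h row is 690-750 min, and the column heading presents these as the elapsed times that are acceptable. The only operating rule after the table is a tie-break, which begins "If there are two or more data points that fit the time window the data point that occurs the closest".

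Section 9.9 lists the ECGs to be summarised: "12-lead ECGs at day 1 Preop (D1 Preop), and 1 hour and 12 hours after study drug administration". Section 9.9.1 gives two outputs. For the tabulation, "The investigator classifications will be tabulated by treatment and overall treatments at any time during the study and each assessment timepoint". For the shifts, "A shift table comparing the investigator classification of the ECG results at baseline to each scheduled timepoint will also be provided". The mock Tables 14.3-1.1 and 14.3-1.2 have separate rows for 1 hour, 12 hours and Any Post-Baseline.

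The schedule in Section 12 gives general windows of ± 10 min at 1 h and ± 30 min at 12 h in its column headings. Footnote 4, attached to the ECG row, replaces these for ECGs: "Postsurgical 12-lead ECGs will be performed at 1 hour (± 15 minutes) and 12 (± 2) hours after study drug administration".

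**The concern.** The SAP permits an ECG to be taken at times that its own analysis table does not recognise. An ECG at 46 min or at 13 h complies with footnote 4, yet matches no row of Table 1. Someone who programs the tables from Section 7 would leave it out of the by-timepoint rows. Someone who programs from the visit label would keep it. The SAP does not say which is intended.

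Only two post-dose ECG timepoints are summarised, in groups of about 15. Section 9.1 bases percentages, unless otherwise noted, on all subjects in the treatment group, and the mock of Table 14.3-1.1 has no line for the number assessed or missing. An ECG left out of a timepoint row would therefore leave the numerator and stay in the denominator, with nothing in that row to show it. One subject in 15 is 1/15 = 6.7 percentage points.

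**Working it through.** **Inputs**

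- Table 1 (Section 7): 1 h = 50-70 min; 12 h = 690-750 min.
- Schedule column windows (Section 12): 1 h ± 10 min; 12 h ± 30 min.
- Footnote 4 (Section 12), ECG only: 1 h ± 15 min; 12 h ± 2 h.
- Time origin: start of study drug in Section 7. The general note under the schedule also counts postsurgical timepoints from the beginning of administration, so a different origin does not explain the gap.

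**Step 1. Reproduce Table 1**

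- 1 h: 60 ± 10 = 50-70 min.
- 12 h: 720 ± 30 = 690-750 min.

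Both match exactly. These two rows follow the general column windows; footnote 4 was not carried over.

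**Step 2. ECG windows from footnote 4**

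- 1 h: 60 ± 15 = 45-75 min, a width of 30 min.
- 12 h: 720 ± 120 = 600-840 min, a width of 240 min.

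**Step 3. Share of the ECG window that Table 1 covers**

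| Timepoint | ECG window | Table 1 | Covered | Not covered |
|---|---|---|---|---|
| 1 h | 45-75 min | 50-70 min | 20/30 = 67% | 10/30 = 33% |
| 12 h | 600-840 min | 690-750 min | 60/240 = 25% | 180/240 = 75% |

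**Step 4. Does another row pick up the remainder?**

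The neighbouring Table 1 rows are 30 min (25-35 min), 2 h (105-135 min), 8 h (450-510 min) and 16 h (15-17 h = 900-1020 min). None overlaps 45-75 or 600-840 min. In a check of every whole minute, 10 of 31 at 1 h and 180 of 241 at 12 h fall in no row, and none falls in a different row. The tie-break does not help, because it chooses only among points that already fit a window.

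**Step 5. What this could mean for subjects at 12 h**

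The shares in Step 3 are shares of window width. Turning them into shares of ECGs needs a timing distribution, which the document does not give. Three assumed cases, centred on 12 h:

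- Normal, SD 15 min: P(|Z| > 30/15) = P(|Z| > 2) = 0.046, about 5%.
- Normal, SD 60 min: P(|Z| > 30/60) = P(|Z| > 0.5) = 0.617. This includes ECGs beyond ± 2 h, which do not comply with footnote 4: P(|Z| > 2) = 0.046. Among compliant ECGs the share is (0.617 − 0.046)/(1 − 0.046) = 0.571/0.954, about 60%.
- Uniform over the permitted window: 180/240 = 75%.

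**Step 6. Are the other Table 1 rows safe to endorse?**

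Not as a group. The 60 h row is 57-63 h, that is ± 3 h, while the schedule column for 60 h is ± 2 h, that is 58-62 h.

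**The case against.** **No sentence discards ECGs.** A reader might infer that the SAP throws away valid safety data. It does not say so. Omission from a timepoint row follows from applying Table 1's acceptable times, not from an explicit instruction. Only the two blood-loss listings relabel out-of-window points as unscheduled; the NRS, circumference and SWAS listings flag them with an asterisk. Listing 16.2-9 shows scheduled timepoint, actual time and deviation, which fits analysis by nominal time. This stands as a limit on the claim. It does not remove the problem, because nominal-time analysis is stated nowhere and Table 1 is introduced for the analyses generally.

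**The ECGs do not vanish.** It is tempting to say that they drop out of the tabulation and the shift table altogether. Both mock tables have Any Post-Baseline rows, in which these ECGs still count, and the listing shows them. Only the 1 hour and 12 hours rows are exposed.

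**The uniform case is not a forecast.** One could turn 75% into roughly 11 of 15 subjects per arm. The document does not support this. ECGs share their scheduled timepoints with vital signs and PK sampling, which carry the tighter column windows, so clustering near the nominal time is plausible. The assumed range at 12 h runs from about 5% to 75%.

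**Footnote 4 may not be the current text.** Section 7 refers to the protocol's schedule for individual windows, and that schedule is not at hand. The copy in the SAP looks partly outdated: it still asks for knee and thigh measurements on both legs, while Section 9.8.6 says Amendment 2 requires only the surgical leg. So a reader should not conclude that footnote 4 is right and Table 1 wrong. What can be said is that they disagree and must be reconciled.

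**Conclusion.** The inconsistency is certain: Table 1 recognises 67% of the ECG window at 1 h and 25% at 12 h, and no other row or rule in the SAP covers the rest. The omission of compliant ECGs from the two timepoint rows is conditional on Table 1 being applied as written. The number of subjects affected cannot be determined from the document; the 12 h figures in the working are scenarios that rest on assumed timing.

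Severity is minor. The output is a three-category investigator reading, Section 9.9 plans no inferential statistics for safety, the primary objective is pharmacokinetic, and the Any Post-Baseline rows and the listing retain the data.

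**What to change.** Do one of the following:

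1. Add a sentence to Section 7 or Section 9.9.1 stating that ECGs are summarised by nominal scheduled timepoint. Listing 16.2-9 already shows actual time and deviation, so departures stay visible.
2. Reconcile footnote 4 and Table 1 with the current protocol, then add ECG-specific 1 h and 12 h rows to Table 1 that match the reconciled ECG windows. If footnote 4 is confirmed, rows of 45-75 min and 600-840 min would overlap no neighbouring Table 1 row.

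Do not add a general statement that the remaining Table 1 rows are correct; the 60 h row should be reconciled with its schedule column in the same pass.

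The cost is one sentence or two table rows. No new data and no change in study conduct are needed.
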